8.3.3.3. Assessment of outcomes

The investigator will assess the outcome of all unsolicited AEs (including SAEs) recorded during the study as:

- Recovered/resolved.
- Recovering/resolving.
- Not recovered/not resolved.
- Recovered with sequelae/resolved with sequelae.
- Fatal (SAEs only).

8.3.3.4. Medically attended visits

For each solicited and unsolicited symptom the subject experiences, the subject's parent(s)/LAR(s) will be asked if the subject received medical attention defined as hospitalization, or an otherwise unscheduled visit to or from medical personnel for any reason, including emergency room visits. This information will be recorded in the eCRF.

8.4. Reporting of serious adverse events

8.4.1. Prompt reporting of serious adverse events to GSK Biologicals

SAEs that occur in the time period defined in Section 8.3 will be reported promptly to GSK within the timeframes described in [Table 15](#), once the investigator determines that the event meets the protocol definition of a SAE.

Table 15 Timeframes for submitting serious adverse events reports to GSK Biologicals

Type of Event	Initial Reports		Follow-up of Relevant Information on a Previous Report	
	Timeframe	Documents	Timeframe	Documents
SAEs	24 hours* [‡]	electronic Expedited Adverse Events Report	24 hours*	electronic Expedited Adverse Events Report

* Timeframe allowed after receipt or awareness of the information.

‡ The investigator will be required to confirm review of the SAE causality by ticking the 'reviewed' box in the electronic Expedited Adverse Events Report within 72 hours of submission of the SAE.

8.4.3. Completion and transmission of SAE reports to GSK Biologicals

Once an investigator becomes aware that a SAE has occurred in a study subject, the investigator (or designate) must complete the information in the electronic Expedited Adverse Events Report **WITHIN 24 HOURS**. The report will always be completed as thoroughly as possible with all available details of the event. Even if the investigator does not have all information regarding a SAE, the report should still be completed within 24 hours. Once additional relevant information is received, the report should be updated **WITHIN 24 HOURS**.

The investigator will always provide an assessment of causality at the time of the initial report. The investigator will be required to confirm the review of the SAE causality by ticking the 'reviewed' box in the electronic Expedited Adverse Events Report within 72 hours of submission of the SAE.

8.4.3.1. Back-up system in case the electronic reporting system does not work

If the electronic reporting system does not work, the investigator (or designate) must complete, then date and sign a paper Expedited Adverse Events Report and fax it to the Study Contact for Reporting SAEs (refer to the [Sponsor Information](#)) or to GSK Biologicals Clinical Safety and Pharmacovigilance department within 24 hours.

This back-up system should only be used if the electronic reporting system is not working and NOT if the system is slow. As soon as the electronic reporting system is working again, the investigator (or designate) must complete the electronic Expedited Adverse Events Report within 24 hours. The final valid information for regulatory reporting will be the information reported through the electronic SAE reporting system.

8.4.4. Updating of SAE information after removal of write access to the subject's eCRF

When additional SAE information is received after removal of the write access to the subject's eCRF, new or updated information should be recorded on the appropriate paper report, with all changes signed and dated by the investigator. The updated report should be faxed to the Study Contact for Reporting SAEs (refer to the [Sponsor Information](#)) or to GSK Biologicals Clinical Safety and Pharmacovigilance department within the designated reporting time frames specified in [Table 15](#).

8.4.5. Regulatory reporting requirements for serious adverse events

The investigator will promptly report all SAEs to GSK in accordance with the procedures detailed in Section [8.4.1](#). GSK Biologicals has a legal responsibility to promptly notify, as appropriate, both the local regulatory authority and other regulatory agencies about the safety of a product under clinical investigation. Prompt notification of SAEs by the investigator to the Study Contact for Reporting SAEs is essential so that legal obligations and ethical responsibilities towards the safety of other subjects are met.

Investigator safety reports are prepared according to the current GSK policy and are forwarded to investigators as necessary. An investigator safety report is prepared for a SAE(s) that is both attributable to the study vaccines and unexpected. The purpose of the report is to fulfil specific regulatory and GCP requirements, regarding the product under investigation.

8.5. Follow-up of adverse events and serious adverse events**8.5.1. Follow-up during the study**

After the initial AE/SAE report, the investigator is required to proactively follow each subject and provide additional relevant information on the subject's condition to GSK Biologicals (within 24 hours for SAEs; refer to [Table 15](#)).

All SAEs documented at a previous visit/contact and designated as not recovered/not resolved or recovering/resolving will be reviewed at subsequent visits/contacts until the last visit of the subject.

All AEs documented at a previous visit/contact and designated as not recovered/not resolved or recovering/resolving will be reviewed at subsequent visits/contacts until 30 days after the last vaccination.

8.5.2. Follow-up after the subject is discharged from the study

The investigator will follow subjects:

- with SAEs, or subjects withdrawn from the study as a result of an AE, until the event has resolved, subsided, stabilised, disappeared, or until the event is otherwise explained, or the subject is lost to follow-up.

If the investigator receives additional relevant information on a previously reported SAE, he/she will provide this information to GSK Biologicals using a paper/electronic Expedited Adverse Events Report and/or pregnancy report as applicable.

GSK Biologicals may request that the investigator performs or arranges the conduct of additional clinical examinations/tests and/or evaluations to elucidate as fully as possible the nature and/or causality of the AE or SAE. The investigator is obliged to assist. If a subject dies during participation in the study or during a recognised follow-up period, GSK Biologicals will be provided with any available post-mortem findings, including histopathology.

8.6. Treatment of adverse events

Treatment of any AE is at the sole discretion of the investigator and according to current good medical practice. Any medication administered for the treatment of a SAE should be recorded in the subject's eCRF (refer to Section 6.7).

8.7. Subject card

Study subjects' parent(s)/LAR(s) must be provided with the address and telephone number of the main contact for information about the clinical study.

The investigator (or designate) must therefore provide a "subject card" to each subject's parent(s)/LAR(s). In an emergency situation this card serves to inform the responsible attending physician that the subject is in a clinical study and that relevant information may be obtained by contacting the investigator.

Subjects' parent(s)/LAR(s) must be instructed to keep subject cards in their possession at all times during the study duration.

9. SUBJECT COMPLETION AND WITHDRAWAL

9.1. Subject completion

A subject who is available for the concluding contact foreseen in the protocol is considered to have completed the study.

9.2. Subject withdrawal

Withdrawals will not be replaced.

9.2.1. Subject withdrawal from the study

From an analysis perspective, a ‘withdrawal’ from the study refers to any subject who was not available for the concluding contact foreseen in the protocol.

All data collected until the date of withdrawal/last contact of the subject will be used for the analysis.

A subject is considered a ‘withdrawal’ from the study when no study procedure has occurred, no follow-up has been performed and no further information has been collected for this subject from the date of withdrawal/last contact.

Investigators will make an attempt to contact those subjects who do not return for scheduled visits or follow-up.

Information relative to the withdrawal will be documented in the eCRF. The investigator will document whether the decision to withdraw a subject from the study was made by the subject’s parent(s)/LAR(s), or by the investigator, as well as which of the following possible reasons was responsible for withdrawal:

- SAE
- Unsolicited non-serious AE
- Solicited AE
- Protocol violation (specify)
- Consent withdrawal, not due to an AE*
- Moved from the study area
- Lost to follow-up
- Other (specify)

*In case a subject is withdrawn from the study because he/she/the subject’s parent(s)/LAR(s) has withdrawn consent, the investigator will document the reason for withdrawal of consent, if specified by the subject/subject’s parent(s)/LAR(s), in the eCRF.

Subjects who are withdrawn from the study because of SAEs/AEs must be clearly distinguished from subjects who are withdrawn for other reasons. Investigators will follow subjects who are withdrawn from the study as result of a SAE/AE until resolution of the event (see Section 8.5.2).

9.2.2. Subject withdrawal from study vaccines

A ‘withdrawal’ from the study vaccines refers to any subject who does not receive the complete treatment, i.e., when no further planned dose is administered from the date of withdrawal. A subject withdrawn from the study vaccines may not necessarily be withdrawn from the study as further study procedures or follow-up may be performed (safety or immunogenicity) if planned in the study protocol.

Information relative to premature discontinuation of the study vaccines will be documented on the Vaccine Administration page/screen of the eCRF. The investigator will document whether the decision to discontinue further vaccination/treatment was made by the subject’s parent(s)/LAR(s), or by the investigator, as well as which of the following possible reasons was responsible for withdrawal:

- SAE
- Unsolicited non-serious AE
- Solicited AE
- Not willing to be vaccinated
- Other (specify)

10. STATISTICAL METHODS

10.1. Primary endpoints

- Immunogenicity with respect to components of the routine infant vaccines, one month after Dose 3 of routine infant vaccines (Visit 4):
 - Anti-D antibody concentration ≥ 0.1 IU/mL,
 - Anti-T antibody concentration ≥ 0.1 IU/mL,
 - Anti-HBs antibody concentrations ≥ 10 mIU/mL,
 - Anti-poliovirus types 1, 2 and 3 antibody titers ≥ 8 ED₅₀,
 - Anti-PT, anti-FHA and anti-PRN antibody concentrations expressed as GMCs,
 - Anti-pneumococcal serotypes (1, 3, 4, 5, 6A, 6B, 7F, 9V, 14, 18C, 19A, 19F, 23F) antibody concentrations expressed as GMCs,
 - Anti-PRP antibody concentrations ≥ 0.15 μ g/mL,
 - Anti-PRP antibody concentrations ≥ 1.0 μ g/mL.
- Difference in seroresponse with respect to PT, FHA and PRN antigen components one month after Dose 3 of routine infant vaccines (Visit 4):
 - Seroresponse to anti-PT, anti-FHA and anti-PRN.

10.2. Secondary endpoints

- Serum anti-rotavirus IgA antibody seropositivity 3 months after Dose 2 of HRV vaccine (Visit 4).
 - Serum anti-RV IgA antibody concentrations ≥ 20 U/mL and ≥ 90 U/mL 1-2 months after Dose 2.
- Immunogenicity with respect to components of the routine infant vaccines, one month after Dose 3 of routine infant vaccines (Visit 4):
 - PT, anti-FHA and anti-PRN antibody concentrations ≥ 2.693 IU/mL, ≥ 2.046 IU/mL and ≥ 2.187 IU/mL, respectively.
 - Anti-pneumococcal serotypes (1, 3, 4, 5, 6A, 6B, 7F, 9V, 14, 18C, 19A, 19F, 23F) antibody concentrations ≥ 0.35 μ g/mL for the ELISA,
 - Anti-D, anti-T, anti-PRP and anti-HBs antibody concentrations expressed as GMCs and anti-poliovirus types 1, 2 and 3 antibody concentrations expressed as Geometric Mean Titers (GMTs).
- Occurrence of general solicited AEs during the 8 day (Day 1-Day 8) follow-up period after each dose of HRV vaccine.
- Occurrence of unsolicited AEs within 31 days (Day 1-Day 31) after any dose of HRV vaccine, according to the Medical Dictionary for Regulatory Activities (MedDRA) classification.
- Occurrence of SAEs from Dose 1 of study vaccines up to study end.

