2.2. Secondary objectives

Immunogenicity:

- To assess the immunogenicity of the PCV-free liquid HRV vaccine and currently licensed lyophilized HRV vaccine in terms of serum anti-rotavirus immunoglobulin A (IgA) antibody seropositivity rate at Visit 4, 3 months after Dose 2 of the HRV vaccine.
- To assess the immunogenicity of routine infant vaccines *Pediarix*, *Hiberix* and *Prevenar 13* when co-administered with the PCV-free liquid HRV vaccine and

[figure not shown]
currently licensed lyophilized HRV vaccine at Visit 4, 1 month after Dose 3 of routine infant vaccines.

Reactogenicity and safety:

- To assess the reactogenicity of the PCV-free liquid HRV vaccine and currently licensed lyophilized HRV vaccine in terms of general solicited adverse events (AEs) during the 8 day (Day 1-Day 8) follow-up period after each dose of HRV vaccine.
- To assess the safety of the study vaccines in terms of unsolicited AEs during the 31 day (Day 1-Day 31) follow-up period after each dose of HRV vaccine and serious adverse events (SAEs) during the entire study period.

Refer to Section 10.2 for the definition of the secondary endpoints.

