Co-administration of routine childhood vaccines *Pediarix*, *Hiberix* and *Prevenar 13* will be performed as follows:

- All the subjects will receive a dose each of *Pediarix*, *Hiberix* and *Prevenar 13* at Visit 1 (Day 1), Visit 2 (Month 2) and Visit 3 (Month 4).
- The routine booster dose for the co-administered vaccines will not be administered to subjects as a part of this study. Subject's parent(s)/LARs will be

reminded at Visit 4 to consult their primary health care provider regarding the booster dose of the vaccines for their child.

- Treatment allocation: Randomized 1:1 using GSK Biologicals' Randomization System on Internet (SBIR).
- Blinding: single-blind

The blinding of the study epoch is provided in [Table 3](#).

Table 3 Blinding of study epoch

Study Epoch	Blinding
Epoch 001	single-blind

- Sampling schedule: Details of the samples to be collected are as follows:
 - Blood samples will be collected from all subjects at Visit 4 (Month 5) to measure serum anti-RV IgA antibody concentrations and antibody concentrations/titers against all the antigens in the co-administered vaccines.
- Type of study: self-contained.
- Data collection: Electronic Case Report Form (eCRF).
- Safety monitoring: An IDMC consisting of clinical experts and a biostatistician will review the safety data by treatment group periodically to monitor the safety aspects of the PCV-free liquid HRV vaccine.

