Post-Vacc = blood sample collected from subjects, one month after the third dose of the co-administered vaccines (Visit 4); ESFU: Extended Safety Follow-up; AE = Adverse Event; SAE = Serious Adverse Events; LAR = Legally Acceptable Representative.

*If regurgitation or vomiting occurs after vaccination, a single replacement dose may be given at the same vaccination visit at the discretion of the Investigator.

Advisory Committee on Immunization Practices (ACIP) recommends administering monovalent Hepatitis B vaccine to all newborns before hospital discharge. Infants who did not receive a birth dose should receive three doses of a Hepatitis-B-containing vaccine on a schedule of 0, 1 to 2 months, and 6 months starting as soon as feasible. Administer the second dose, 1 to 2 months after the first dose (minimum interval of four weeks), administer the third dose at least eight weeks after the second dose AND at least 16 weeks after the first dose. The final (third or fourth) dose in the Hepatitis B vaccine series should be administered no earlier than age 24 weeks.

Whenever possible, the investigator should arrange study visits within the interval described in [Table 5](#).

Table 5 Intervals between study visits

Interval	Optimal length of interval
Visit 1→Visit 2	60 days
Visit 2→Visit 3	60 days
Visit 3→Visit 4	30 days
Visit 3→ESFU ‡	6 months

‡A safety follow-up contact (by telephone call or any other convenient procedure) to collect information on SAEs and medication taken for treatment of the same.

Refer to [Table 19](#) for intervals between study visits that determine subjects' eligibility for inclusion in the per-protocol analysis.

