10.4.2. Per-protocol Set for analysis of immunogenicity

The PPS for immunogenicity will include all eligible subjects from the ES:

- who have received the study vaccines according to their random assignment,
- who comply with the vaccination schedule of routine infant vaccines and HRV vaccines as per [Table 19](#),
- for whom the routine infant vaccines were administered according to the protocol as per [Table 10](#),
- for whom the HRV vaccine liquid or lyophilized formulation was administered according to protocol,
- who have not received a vaccine not specified or forbidden in the protocol up to Visit 4 blood sampling,
- who had not received medication forbidden by the protocol up to Visit 4 blood sampling,
- whose underlying medical condition(s) was (were) not forbidden by the protocol up to Visit 4 blood sample,
- for whom data concerning immunogenicity endpoint measures are available. This will include subjects for whom assay results are available for antibodies against at least one routine infant vaccine antigen component,
- who comply with the blood sampling schedule after the 3rd dose of Pediarix, Hiberix and Prevenar 13 as per [Table 19](#),
- who have no concomitant infection up to Visit 4 blood sample, which may influence the immune system.

Table 19 Maximum allowed interval between visits

Interval	Allowed length of interval
Visit 1 → Visit 2	49 days-83 days after Dose 1 of study vaccines 1
Visit 2 → Visit 3	56 days-83 days after Dose 2 of study vaccines 1
Visit 3 → Visit 4	21 days-48 days after Dose 3 of study vaccines 1
Visit 3 → ESFU	180 days-210 days after Dose 3 of study vaccines

¹ Subjects will not be eligible for inclusion in the Per-Protocol Set (PPS) for analysis of immunogenicity, if they make the study visit outside this interval. This is not applicable for the interval between Visit 3 and ESFU.

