10.7.1. Within group analysis

For each treatment group, one month after Dose 3 of routine infant vaccines at Visit 4 (Month 5) time-point:

- Seroprotection rates against HBsAg, diphtheria toxoid, tetanus toxoid, PRP antigen and poliovirus types 1, 2 and 3 (with exact 95% CI) will be calculated.
- Seropositivity rates and their exact 95% CIs for antibodies against PT, FHA, PRN, anti-rotavirus, S. pneumoniae serotypes 1, 3, 4, 5, 6A, 6B, 7F, 9V, 14, 18C, 19A, 19F, 23F and HBsAg will be tabulated.
- Percentage of subjects with anti-pneumococcal serotypes (1, 3, 4, 5, 6A, 6B, 7F, 9V, 14, 18C, 19A, 19F, 23F) antibody concentrations $\geq 0.35 \mu\text{g/mL}$ with 95% CI will be calculated.

- Percentage of subjects with anti-PRP antibody concentrations $\geq 1.0 \mu\text{g/mL}$ will be calculated with 95% CI.
- Percentage of subjects with anti RV IgA antibody concentration $\geq 90 \text{ U/mL}$ will be calculated with 95% CI.
- GMC/GMT with 95% CI will be tabulated for antibodies against each antigen.

The above mentioned descriptive analyses will also be performed by race and sex.

The distribution of antibody concentrations/titers for each appropriate serotype/antigen will be displayed using tables and/or reverse cumulative distribution curves.

For anti-HBs antibodies, an analysis will be done according to vaccination history to Hepatitis B vaccine.

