6.3.1.1. Within group analysis

For each treatment group, one month after Dose 3 of routine infant vaccines at Visit 4 (Month 5) time-point:

- Seroprotection rates against HBsAg, diphtheria toxoid, tetanus toxoid, PRP antigen and poliovirus types 1, 2 and 3 (with exact 95% CI) will be calculated.
- Seropositivity rates and their exact 95% CIs for antibodies against PT, FHA, PRN, anti-rotavirus, S. pneumoniae serotypes 1, 3, 4, 5, 6A, 6B, 7F, 9V, 14, 18C, 19A, 19F, 23F and HBsAg will be tabulated.
- Percentage of subjects with anti-pneumococcal serotypes (1, 3, 4, 5, 6A, 6B, 7F, 9V, 14, 18C, 19A, 19F, 23F) antibody concentrations $\geq 0.35 \mu\text{g/mL}$ with 95% CI will be calculated.
- Percentage of subjects with anti-PRP antibody concentrations $\geq 1.0 \mu\text{g/mL}$ will be calculated with 95% CI.

- Percentage of subjects with anti RV IgA antibody concentration ≥ 90 U/mL will be calculated with 95% CI.
- GMC/GMT with 95% CI will be tabulated for antibodies against each antigen.

The above mentioned descriptive analyses will also be performed by race and sex.

The distribution of antibody concentrations/titers for each appropriate serotype/antigen will be displayed using tables and/or reverse cumulative distribution curves.

For anti-HBs antibodies, an analysis will be done according to vaccination history to Hepatitis B vaccine.

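### Does the 1–2 month time point for the anti-rotavirus IgA cut-offs leave a secondary endpoint without a sample?

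*Protocol*

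**What the plan says.** The secondary endpoints in Protocol section 10.2 open with a parent line, "Serum anti-rotavirus IgA antibody seropositivity 3 months after Dose 2 of HRV vaccine (Visit 4", followed by a sub-item, "Serum anti-RV IgA antibody concentrations ≥ 20 U/mL and ≥ 90 U/mL 1-2 months after Dose 2". The same pair stands in the Protocol synopsis and in SAP section 4.2.

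The other statements on timing are these:

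- Protocol section 2.2 (and SAP section 3.2) states the objective as the "antibody seropositivity rate at Visit 4, 3 months after Dose 2 of the HRV vaccine".
- Protocol section 3, under the sampling schedule: "Blood samples will be collected from all subjects at Visit 4 (Month 5) to measure serum anti-RV IgA antibody concentrations". Table 4, section 5.6.9.1, Table 6 and Table 8 list no other blood sample, and the SAP repeats the schedule in section 2.
- Protocol section 10.7.1 puts all within-group immunogenicity summaries "one month after Dose 3 of routine infant vaccines at Visit 4 (Month 5) time-point". SAP section 6.3.1.1 uses the same heading and includes under it: "Percentage of subjects with anti RV IgA antibody concentration ≥ 90 U/mL will be calculated with 95% CI".
- Protocol Table 7 sets the rotavirus IgA cut-off at 20 U/mL. Section 10.5 defines a seropositive subject as one at or above the cut-off in that table.

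**The concern.** Two consecutive lines give different times for results from the same assay. Read literally, the sub-item defines an endpoint at a time when no sample is scheduled, so the 20 and 90 U/mL percentages would have no data behind them. The slip appears in three places, one of them the SAP, and it concerns the response to the investigational vaccine itself.

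The practical risk is mislabelling. If the sub-item were copied into a table title, the study report or a public posting, a 3-month value would be read as a 1–2 month value. Some mock tables in SAP Annex 3 carry similar labels: Template 11 is titled for one month after the second dose, and a footnote in the same annex describes a sample at Visit 3 one month after that dose. An analyst could take these as agreeing with the sub-item.

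**Working it through.** **Inputs.** The second HRV dose is given at Visit 2, Month 2 (Protocol Tables 4 and 10). Blood is drawn at Visit 4, Month 5 (Protocol section 3, Tables 4 and 6). Table 5 (section 5.5), in the column "Optimal length of interval", gives 60 days from Visit 2 to Visit 3 and 30 days from Visit 3 to Visit 4. Table 19 (section 10.4.2) allows "56 days-83 days after Dose 2 of study vaccines 1" for Visit 2 to Visit 3 (the final 1 is a footnote mark) and 21 to 48 days for Visit 3 to Visit 4.

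**Reproducing the plan's 3 months.** Month 5 − Month 2 = 3 months. In days, at the optimal spacing, 60 + 30 = 90.

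**Per-protocol range.** Earliest: 56 + 21 = 77 days. Latest: 83 + 48 = 131 days.

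**The interval in the sub-item.** With a month taken as 30.4375 days, 1–2 months is 30.4 to 60.9 days.

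| Visit 4 sample | Days after HRV Dose 2 | Days beyond 2 months |
|---|---|---|
| Earliest per-protocol | 77 | 77 − 60.9 = 16.1 |
| Optimal spacing | 90 | 90 − 60.9 = 29.1 |
| Latest per-protocol | 131 | 131 − 60.9 = 70.1 |

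No per-protocol sample can fall within 1–2 months. The Exposed Set is not bound by Table 19, but its only scheduled sample is also Visit 4.

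**Alternative readings.** Reading Dose 2 as the second dose of the routine vaccines does not help, because that dose is also given at Visit 2. Visit 3 is about 60 days after Visit 2 and would fit the interval, but no blood is taken there. The sub-item is therefore simply wrong about the time.

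**What depends on it.** The sub-item carries two cut-offs.

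- *20 U/mL.* By Protocol section 10.5 and Table 7, being at or above 20 U/mL is seropositivity. The parent line already defines that endpoint at Visit 4. The sub-item repeats it with a wrong time and adds no second quantity.
- *90 U/mL.* Within the endpoint list, this percentage appears only in the sub-item. Protocol section 10.7.1 and SAP section 6.3.1.1 specify its calculation under the Visit 4 heading.

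Both percentages are thus fixed at Visit 4 by the text that governs the analysis. Rotavirus IgA geometric means fall under the same heading, since GMCs are tabulated there for every antigen.

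**Effect on inference.** Protocol section 10.9 and SAP section 7 treat everything outside the co-primary criteria as descriptive. Rotavirus IgA has no row in the power table (Table 18) and no place in the hierarchical testing. Both groups follow the same visit schedule, so a wrong label would affect them equally.

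**The case for a change.** The strongest case for acting is that an endpoint definition should not name a time at which nothing is measured, least of all for the vaccine under test. The correction would be a few words, the documents themselves show what those words should be, and Protocol section 11.5 commits the sponsor to public posting of secondary results. The carried-over labels in SAP Annex 3 make a mislabelled table more plausible.

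Some of this stands: the text is inconsistent, it is not an artefact of extraction, and whoever writes the report or the posting must label the result as Visit 4. The rest carries less weight. The correct time is one line above the wrong one and again in the objective. No site or laboratory could act on the sub-item, because the procedures table contains no such draw. The Annex 3 shells plainly come from other studies: Template 11 compares three lots of the liquid vaccine, which this two-group trial does not do. An analyst must adapt their titles and footnotes anyway. Nor is a correction quite free, since two of the three instances are in the Protocol and amendments go through ethics review (section 5.1).

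A related wording difference adds nothing of substance. SAP section 11.2.4 describes rotavirus IgA seropositivity as a concentration above 20 U/mL, whereas the endpoint and Protocol section 10.5 include the value 20. Only a result of exactly 20 U/mL would be classified differently.

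**Conclusion.** The inconsistency is real but clerical, and no change to the plan follows. The sub-item is the outlier against the parent line, the objective, the single blood draw and both analysis sections, so the intended time point is not in doubt. The mismatch is about 29 days at the optimal spacing and at least 16 days for any per-protocol sample. That measures how wrong the label is; the effect on any estimate, interval or group comparison is nil. Correcting the wording would alter neither what is sampled nor what is calculated or concluded.

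This rests on three points: Visit 4 remains the only blood draw, the analysis sections and not the endpoint sub-item drive the programming, and the rotavirus IgA results stay descriptive. All three are what the Protocol and SAP now say.
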